5.2 Trial Treatments

The treatments to be used in this trial are outlined below in Table 3

Table 3 Trial Treatment

Drug	Dose/ Potency	Dose Frequency	Route of Delivery	Regimen/Treatment Period	Use
pembrolizumab	200 mg	Q3W	IV infusion	4 cycles per course	Experimental
Aldesleukin	250,000 or 125,000 U/kg	Daily 5days/7	SQ	1 six-week cycle per course	Non-Standard Dose and Schedule
Aldesleukin	72,000 U/kg	Q8 hrs x 14 doses	IV	2 cycles per course	Non-Standard Dose
Aldesleukin	600,000 U/kg	Q8 hrs x 14 doses	IV	2 cycles per course	Standard
The pembrolizumab dosing interval may be increased due to toxicity as described in Section 5.2.1.2.					

5.2.1 Dose Selection/Modification

5.2.1.1 Dose Selection

The rationale for selection of doses to be used in this trial is provided in Section 4.0 – Background and Rationale.

5.2.1.2 Rules for Dose Escalation

Dose-limiting toxicities (DLT's) observed in course 1 will be used to determine escalation to the next dose level. A course is 12 weeks. The study will use a 3 + 3 trial design for IL-2 dose escalation. The first 3 patients will be enrolled at Dose Level 1. If no dose-limiting toxicities (DLT's) occur in the first 3 patients over treatment course 1, Dose Level 2 will then open for enrollment of the next 3 patients. In the absence of DLT's in three patients treated at Dose Level 2, then Dose Level 3 will open for enrollment of the next 3 patients.

If 1 of 3 subjects in a cohort experiences a DLT, the Cohort will expand to 6 pts. If only 1 of 6 patients experiences a DLT with all patients followed for safety endpoints to the end of course 1, then the next cohort dose level will open to enroll.

If two or more patients in a cohort experience a DLT, that dose level exceeds the MTD.

If two or more delayed DLT's (i.e., DLT's that occur after course 1) are noted within a dose-escalation cohort, accrual will be held pending safety analysis by the Principal Investigator and Merck and restarted only with Principal Investigator and Sponsor approvals with IRB and FDA notification.

Dose escalations or de-escalations of pembrolizumab are not allowed. Treatment delays for toxicity are allowable as described in [Section 5.2.1.4](#). Patients enrolled into Dose Level 3 who require treatment interruption and meet restarting criteria as described in [Section 5.2.1.4](#) may have IL-2 dosing de-escalated to the IV IL-2 Dose Level 2 for the subsequent treatment cycle and/or course(s) 2 and/or 3. Individual patient IL-2 dosing cannot be escalated.

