5.2.1.3 Definition of Dose-Limiting Toxicities

All toxicities will be graded using the National Cancer Institute (NCI) CTCAE v5.0 (Appendix 2; Section 13.2). Dose-limiting toxicity (DLT) assessment will be based on events occurring during the DLT assessment period, which is defined as course 1. Dose-limiting toxicities include all adverse experiences that are clearly not related to disease progression or intercurrent illness if judged by the investigator to be possibly, probably, or definitely related to study treatments that meet or exceed the following severity criteria:

- Toxicities associated with pembrolizumab representing autoimmune phenomenon have been extensively characterized, and may be exacerbated by combination treatment with IL-2. Treatment associated AE's that represent immune mediated pathology are codified in [Section 5.2.1.4](#), Table 4. For patients at Dose Level 1, all AE's resulting in Guideline recommendation for Treatment Discontinuation will also constitute a DLT.
- A delay in the scheduled administration of either component of therapy of > 21 days for pembrolizumab or SQ or IV bolus IL-2.
- Bolus IV dosing of IL-2 (Dose Level 2 and 3), especially at Dose Level 3, is known to be associated with acute severe toxicities. Doses are administered to patient tolerance according to established treatment guidelines (Appendix 4, Section 13.4). Toxicities associated with IL-2 administration will be initially managed according to the IL-2 Toxicity Management Guidelines (Appendix 4, Section 13.4). Toxicities that fail to stabilize within 48 hours of the last IL-2 dose or that fail to show improvement within 72 hours of the last IL-2 dose will convert to management according to [Section 5.2.1.4](#), Table 4 and resulting AE grade and Treatment Discontinuation assignment forming the basis for DLT determination.
- Grade 5 toxicity

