8.1.1 Accrual and Study Progress Oversight

The Principal Investigator will direct the formation of a Safety Data Review Board (SDRB) that will review study accrual and provide direction for dose escalations based on analysis of collected safety data including AE's, SAE's and DLT's. The SDRB will consist of the Principal Investigator, designated sub-investigators, and study administrative staff. Meetings will occur after completion of each dose-level cohort and on an as needed basis to address unanticipated adverse events. Meeting minutes will be documented. Any significant safety findings will be reported to Fred Hutch/University of Washington Cancer Consortium Institutional Review Board (IRB).

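### A single treatment-related death counts as one ordinary DLT, and no written rule holds accrual after it, either at the 3-to-6 expansion or after course 1

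*Combined protocol and SAP*

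**What the plan says.** Section 5.2.1.3 limits the DLT window: "Dose-limiting toxicity (DLT) assessment will be based on events occurring during the DLT assessment period, which is defined as course 1". Course 1 is 12 weeks. An event counts if it is "judged by the investigator to be possibly, probably, or definitely related to study treatments" and meets one of four criteria. The last is "Grade 5 toxicity"; another is a delay of more than 21 days in either drug. All four carry the same weight.

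Section 5.2.1.2 sets the consequences:

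- One DLT in three: "If 1 of 3 subjects in a cohort experiences a DLT, the Cohort will expand to 6 pts".
- One in six, once every patient has been observed through course 1: "then the next cohort dose level will open to enroll".
- Two or more patients with a DLT: the level is above the MTD.
- Two or more DLTs after course 1 within an escalation cohort: "accrual will be held pending safety analysis by the Principal Investigator and Merck". Restart needs Principal Investigator and Sponsor approval, with the IRB and FDA notified. This is the only accrual hold written in the protocol.

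Section 8.1.1 makes the SDRB (the Principal Investigator, sub-investigators and study staff) responsible for directing escalation. On timing: "Meetings will occur after completion of each dose-level cohort and on an as needed basis to address unanticipated adverse events".

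**The concern.** In a phase I trial whose primary objective is safety, one would expect the plan to say whether enrolment stops after a treatment-related death. Here a death is handled by counting rules that do not distinguish it from a scheduling delay. Two places are exposed: the step from three to six patients at the same dose, and the period after course 1. Treatment can run to three 12-week courses, so up to 24 of 36 weeks (two-thirds) lie outside the DLT window, and Section 5.2.1.4 warns that pembrolizumab events may appear months after the last dose.

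The rules are also out of order by severity. Two non-fatal delayed DLTs in a cohort stop accrual and require defined approvals to restart; one late related death does neither. New patients could be enrolled before any required review of the death had taken place.

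**Working it through.** The documents give no operating characteristics for the escalation rule, so there is no figure of the plan's own to reproduce. The check traces the rules and then illustrates their size with assumed risks.

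**Rule trace for one related Grade 5 event**

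| When it occurs | Written consequence | Mandatory hold? | Scheduled SDRB meeting first? |
|---|---|---|---|
| Course 1, first 3 patients, only DLT | Three more patients at the same level | No | No; the meeting follows cohort completion |
| Course 1, still the only DLT in 6 | Next level opens once all six are followed through course 1 (Dose Levels 1 and 2 only) | No | Yes |
| After course 1, only delayed DLT | None | No; threshold is two | None tied to the event |

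The 1-of-6 rule requires follow-up through course 1 before it acts. The 1-of-3 expansion rule states no such condition.

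**Other sections that might supply a hold**

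- 7.3.3.1 and 7.3.5: prompt reporting, with no accrual action attached.
- 8.1.1: ad hoc SDRB meetings as needed for unanticipated events; a Grade 5 event is not named as a trigger.
- 8.1.2: committee review at least annually and as needed. It mentions stopping rules, but the protocol writes none for a death.
- 5.8 and 11.0: termination on unquantified grounds.

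**Illustration, course 1.** Let q be the per-patient risk of a related death and d the risk of any other DLT. Both are assumed.

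- P(at least one death in 3) = 1 − (1 − q)³.
- P(the death is the only DLT, so the cohort expands) = 3q(1 − q − d)².
- At q = 0.05 and d = 0.10: 1 − 0.95³ = 0.143, and 3 × 0.05 × 0.85² = 0.108. The ratio is 0.760, so 76% of cohorts with a death in the first three expand. The rest have two or more DLTs and exceed the MTD.
- Over q = 0.01 to 0.15 and d = 0 to 0.20, the ratio runs from 49% to 99%.
- No further DLT in the next three: 0.85³ = 0.614. Then 0.760 × 0.614 = 0.467, so 47% would also meet the written 1-of-6 criterion (14–96% over the same range), subject to the SDRB meeting.

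**Illustration, after course 1.** Let r be the assumed per-patient risk of a late related death, counting deaths alone.

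| Cohort size, r | P(at least 1) | P(at least 2, hold) | P(exactly 1) | Share of cohorts with a late death but no hold |
|---|---|---|---|---|
| 3, 5% | 0.143 | 0.007 | 0.135 | 95% |
| 6, 5% | 0.265 | 0.033 | 0.232 | 88% |
| 3, 10% | 0.271 | 0.028 | 0.243 | 90% |
| 6, 10% | 0.469 | 0.114 | 0.354 | 76% |

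For six patients at 5%: 1 − 0.95⁶ = 0.265; 6 × 0.05 × 0.95⁵ = 0.232; 0.232/0.265 = 0.88. Non-fatal delayed DLTs in the same cohort would make the hold more likely, so these shares are upper values.

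**The case against.** Weighting all DLTs equally is how a 3+3 design works, and the sections do not contradict each other. A death is far from invisible. Section 7.3.3.1 sends it to the Sponsor within 24 hours and to Merck within 2 working days, with expedited reports to FDA as required. Section 7.3.5 covers regulators and IRBs, and Section 8.1.1 sends significant safety findings to the IRB. Section 8.1.2 makes applicable committee approval a condition of continuing, and Sections 8.1, 5.8 and 11.0 give routes to closure. Section 8.1.2 also relies on an institutional Data and Safety Monitoring Plan (DSMP), not available here, that may contain a rule for deaths.

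Most of this stands, and it rules out several stronger readings:

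- A reader might infer that the trial can escalate after a death with no pause at all. It cannot: at 1 of 6, all six must be followed through course 1, and an SDRB meeting is planned at cohort completion.
- A reader might infer that nobody outside the study team would learn of the death before enrolment continued. The reporting provisions do not support that. They do not require anyone outside to finish a review first, which is a narrower gap.
- A reader might infer that a death from a known IL-2 toxicity would be classed as anticipated and so bypass the SDRB. No section classes any death that way.
- A reader might size the escalation risk by the chance of any related death in 12 to 15 patients: 11–14% at an assumed 1% risk (1 − 0.99¹² to 1 − 0.99¹⁵). That counts Dose Level 3 patients, for whom there is no next level.

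What the objection does not supply is a section that ties accrual to a single death. Reporting is not a hold, discretionary review is not an obligation, and the SDRB's members all belong to the study team.

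**Conclusion.** The point holds in a limited form. As written, one related death in the first three patients leads to enrolment of three more at the same dose. One related death after course 1 counts toward no escalation rule and does not reach the only accrual hold. Neither requires a pause or a completed review before further enrolment. At Dose Level 3 only the expansion and late-death parts apply.

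The conclusion rests on the rule text, not on the probabilities. All risks used above are assumed because the documents give none for this combination, and the 47% figure is the ordinary 3+3 pass probability applied to a cohort that has had a death. The illustrations show only that the gap would be the usual outcome, not a rare one, if a related death occurred. The finding is about the protocol text and does not claim that the institutional DSMP is silent. It is a low-cost improvement that should be made.

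**What to change.** Reconcile Sections 5.2.1.2, 5.2.1.3, 8.1.1 and 8.1.2 so that the protocol states what happens to accrual after one related death:

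- In 5.2.1.2, extend the existing hold to any single Grade 5 event judged at least possibly related to study treatment, in any course or when reported later under 7.3.3.1. Enrolment, including the 3-to-6 expansion, and the opening of any new level are held until the SDRB and the existing Consortium Data and Safety Monitoring Committee have reviewed the event.
- Restart uses the approvals and the IRB and FDA notification already written for delayed DLTs.
- In 8.1.1, name Grade 5 events among the triggers for an ad hoc SDRB meeting. A meeting for every DLT is not needed on this argument.
- In 8.1.2, say which stopping rules the committees evaluate, or cite the part of the institutional DSMP that holds them. If it already has a rule for deaths, a cross-reference and alignment may be enough.

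The change concerns enrolment and oversight only and leaves dosing and patient care untouched. It costs about one paragraph in an amendment and uses committees and notifications that already exist. The downside is a short accrual pause if a related death occurs.

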2.0 TRIAL DESIGN

2.1 Trial Design

This is a phase I, open-label, dose escalation and conditional cohort expansion at the maximum tolerated dose (MTD) of Interleukin-2 (IL-2; aldesleukin), a soluble cytokine growth factor for T lymphocytes, in combination with pembrolizumab (MK-3475), a humanized monoclonal antibody (mAb) of the IgG4/kappa isotype designed to target the Programmed Death 1 (PD1) membrane receptor on activated T lymphocytes. Treatment is for patients with advanced or metastatic clear cell renal cell carcinoma (RCC).

The study will consist of 3 periods: Screening (up to 28 days), Treatment (up to three 12-week courses), and Follow-Up (up to 1 year). Each treatment course (“course” nomenclature is by the conventions of IL-2 treatment) is comprised of 4 doses (cycles) of pembrolizumab given by iv infusion every 3 weeks combined with 1 cycle of IL-2 given by SQ administration daily 5 days/week for 6 weeks at Dose Level 1; or by IV bolus infusion (Dose Level 2 and 3) every 8 hours to a maximum of 14 doses on weeks 1 (cycle 1) and 4 (cycle 2) of a treatment course. Investigator tumor response assessment (by RECIST v1.1) must be completed before the first dose of the next treatment course. The maximum number of on-study treatment courses will be three.

Following completion of treatment, patients with ongoing disease control (CR, PR, or SD) will enter Surveillance Follow-Up. Disease status will be reassessed every 3 months for up to 1-year duration. Patients with disease control completing one year of Surveillance Follow-Up or patients with disease progression will enter Survival Follow-Up to study completion.

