2.2 Dose Escalation

The study will use a 3 + 3 trial design for IL-2 dose escalation. Rules for dose escalations are described in [Section 5.2.1.2](#). Definitions for dose-limiting toxicities (DLT's) are described in [Section 5.2.1.3](#).

[figure not shown]

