2.3 Cohort Expansion

On completion of Dose Escalation including data and safety analysis, the Principal Investigator and Merck will assess the feasibility to enroll additional patients at Dose Level 3 (or at the MTD Dose Level) to gain further preliminary insight into anti-tumor efficacy. Commitment to open the Expansion Cohort and modification of the target enrollment will require protocol amendment.

Table 1 Drug Dose and Schedule

Cohort	Pembrolizumab	IL-2	
1	200 mg Q3W	250,000 U/kg/dose 5 days/wk; wk 1; 125,000 U/kg/dose 5 days/wk; wks 2-6	SQ Dose Level 1
2	200 mg Q3W	72,000 U/kg iv q 8 hrs x 14 doses; d2-6 and 23-27 of a 12 week course	IV Bolus Dose Level 2
3	200 mg Q3W	600,000 U/kg iv q 8 hrs x 14 doses; d2-6 and 23-27 of a 12 week course	IV Bolus Dose Level 3

Figure 1 Trial Diagram

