3.0 OBJECTIVES

The purpose of this study is to characterize the safety, tolerability, preliminary anti-tumor activity, and immunoregulatory (pharmacodynamic) activity of pembrolizumab in combination with IL-2 in patients with metastatic clear cell RCC. The goal of this study is to demonstrate adequate safety and tolerability of the combination of pembrolizumab and IL-2 so as to permit further testing. Information gathered will inform the dose and schedule of administration of pembrolizumab with IL-2 in future studies.

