Recombinant human IL-2 (aldesleukin), a potent growth and differentiation factor for T and NK cells was first explored as a cancer therapy in the mid 1980's by investigators at the National Cancer Institute (NCI) Surgery Branch and subsequently other institutions. Dose escalation studies identified the highest tolerable doses of IL-2 administered as an IV bolus on an every 8 hour schedule. Treatment with 720,000 U/kg or 600,000 U/kg by IV bolus every 8 hours to tolerance and a maximum of 14 doses on weeks 1 and 3 of a treatment course represented the high dose (HD) IL-2 regimen that received FDA approval for the treatment of metastatic RCC in 1992. Approval was based on pooled results of 255 patients treated as part of seven phase II clinical trials conducted at 21 institutions. Patients received from 1 to 3 courses of therapy in total. The overall objective response rate (ORR) was 14% with 5% complete responders (CRs) [19]. Most remarkable was the durability of CRs following IL-2 therapy. For example, the long term follow-up of 259 RCC patients treated by HD IL-2 at the National Cancer Institute Surgery Branch noted recurrent disease in only 4 of 23 patients (17%) who achieved a CR with a median duration of ongoing CR > 11 years at the time of reporting [20].

Despite acute and severe toxicities associated with administration of HD IL-2 necessitating inpatient and typically ICU-level care, the unique potential to achieve unmaintained CRs in RCC patients has sustained HD IL-2 as a viable first-line treatment option for highly selected RCC

patients even in the face of competition from the more recently available targeted therapies that are delivered in an outpatient setting.

Alternate doses and schedules for IL-2 have also been investigated with the goal of avoiding severe toxicity and potentially the need for inpatient administration. In a moderate size phase II study with 27 RCC patients, subcutaneous (SQ) IL-2 given once daily, 5 days per week for 6 weeks in a fully outpatient setting observed an ORR of 23 % including 8% CR [21].

Investigators at the NCI subsequently conducted a randomized, 3-arm trial to compare HD IL-2 with low dose IL-2 regimens given as SQ dosing 5 days/week for 6 weeks, or 72,000 U/kg by IV bolus on a schedule of every 8 hours administration as for the standardized HD regimen.

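### The written escalation rules do not give the stated 12 to 15 patients or say what establishes the MTD; the level carried forward can rest on 0 of 3

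*Combined protocol and SAP*

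**What the plan says.** Section 2.2 of the protocol points to 5.2.1.2 for the rules: "Rules for dose escalations are described in" that section. Section 5.2.1.2 names a 3+3 design over three IL-2 levels and starts each level with three patients. After no DLT in three, the next level opens; for the last step, "then Dose Level 3 will open for enrollment of the next 3 patients". Patients 4 to 6 are added in one case only: "If 1 of 3 subjects in a cohort experiences a DLT, the Cohort will expand to 6 pts". One DLT in six opens the next level. The upper boundary reads: "If two or more patients in a cohort experience a DLT, that dose level exceeds the MTD".

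Section 2.1 describes a "conditional cohort expansion at the maximum tolerated dose (MTD) of Interleukin-2", and section 2.3 refers to an MTD level for that expansion. Neither defines it. On whether expansion patients count toward the current total, section 2.3 says: "Commitment to open the Expansion Cohort and modification of the target enrollment will require protocol amendment".

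Section 1.0 gives the number of subjects as 12 to 15. Section 9.1 makes the toxicity analysis descriptive and gives no sample-size derivation for the escalation. Section 3.0 states the purpose: "Information gathered will inform the dose and schedule of administration of pembrolizumab with IL-2 in future studies".

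**The concern.** Safety and tolerability is the primary objective, and the escalation rules decide how many patients support the dose taken into later work. The prose leaves three things open: what happens after 0 of 3 at Dose Level 3, whether a lower level is filled to six once the level above is too toxic, and what result establishes the MTD. A team following 5.2.1.2 to the letter can therefore finish with three patients at the level carried forward.

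The stated enrolment does not settle the question, because it does not follow from the rules. The expansion cohort cannot supply the difference, since section 2.3 makes it subject to an amendment.

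**Working it through.** **Inputs.** From 5.2.1.2: three levels; three patients first; 0/3 passes; 1/3 expands to six; 1/6 passes; two or more DLTs means the level fails. From section 1.0: N = 12 to 15. The plan gives no DLT rates, so those used in step 2 are assumptions.

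**1. Total N.** Each opened level treats 3 or 6.

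- All three levels opened, with k of them expanded: N = 9 + 3k, so 9, 12, 15 or 18.
- Stopped at level 2: 6, 9 or 12. Stopped at level 1: 3 or 6.

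The stated 12 to 15 is not reproduced at either end (9 and 18 with all levels opened). If six are required at the last level, the minimum with all levels opened is 3 + 3 + 6 = 12, which matches the stated floor. The maximum is still 6 + 6 + 6 = 18, not 15.

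**2. How often it matters.** I enumerated all paths exactly. A cohort with 2 or 3 DLTs in its first three stops at three, and the level carried forward is the highest that passed. The fixed version requires six at that level and steps down if two or more of the six have a DLT.

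| DLT rates, levels 1/2/3 | Mean N, written → fixed | P(N<12), written → fixed | P(N 12–15), written → fixed | Carried forward on 3 patients, as written |
|---|---|---|---|---|
| 5/10/20% | 10.70 → 13.05 | 0.495 → 0.054 | 0.497 → 0.903 | 0.739 |
| 5/15/30% | 10.70 → 13.09 | 0.488 → 0.086 | 0.502 → 0.859 | 0.734 |
| 5/10/40% | 10.83 → 13.31 | 0.465 → 0.054 | 0.526 → 0.891 | 0.761 |
| 5/20/40% | 10.41 → 12.86 | 0.538 → 0.128 | 0.452 → 0.814 | 0.743 |
| 10/20/30% | 10.27 → 12.44 | 0.533 → 0.188 | 0.451 → 0.737 | 0.667 |
| 10/20/50% | 10.14 → 12.36 | 0.558 → 0.188 | 0.429 → 0.744 | 0.677 |
| 20/30/40% | 8.72 → 10.37 | 0.693 → 0.444 | 0.295 → 0.493 | 0.502 |

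The last column is a share of all trials; among trials that carry a level forward it is 71% to 78%. P(N>15) is 0.008 to 0.015 as written and 0.043 to 0.074 fixed. With the fix, every trial that opens Dose Level 3 enrols 12, 15 or 18; all trials below 12 stopped before that level.

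**3. Chance that a level with true DLT rate p passes.** As written: (1−p)³ + 3p(1−p)⁵. With six treated: (1−p)⁶ + 6p(1−p)⁵.

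| p | 0.1 | 0.2 | 0.3 | 0.4 | 0.5 |
|---|---|---|---|---|---|
| As written | 0.906 | 0.709 | 0.494 | 0.309 | 0.172 |
| Six treated | 0.886 | 0.655 | 0.420 | 0.233 | 0.109 |

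**4. What the data would exclude.** The Clopper–Pearson one-sided 95% upper limit for 0/n is 1 − 0.05^(1/n): 0/3 gives 0.632 and 0/6 gives 0.393. For 1/6, solving (1−p)⁶ + 6p(1−p)⁵ = 0.05 gives 0.582.

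**The case against.** The strongest reply is that this is a drafting gap. The trial diagram (Figure 1, in the dose-escalation part of section 2) could not be read in the copy reviewed and may show six patients at the last level. The plan names a 3+3 design, and a reader can infer that the MTD is the highest level not exceeded. Nothing moves forward automatically: section 2.3 requires a data and safety analysis and an amendment before expansion, and the Safety Data Review Board meets after each cohort (8.1.1).

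Dose Level 3 is also familiar as a single agent. Section 4.1.2 says that 600,000 or 720,000 U/kg by IV bolus every 8 hours "represented the high dose (HD) IL-2 regimen that received FDA approval for the treatment of metastatic RCC in 1992". A single-arm study of pembrolizumab with high-dose IL-2, cited in 4.2.1, met no treatment-limiting toxicity and saw responses in 20 of 26 patients. Finally, the 50% to 76% figure pools all levels. Dose Level 3 itself rests on 0/3 in about 8% to 45% of trials under the same profiles; the remainder are lower levels kept after a higher one failed.

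Much of this stands and limits the severity. The diagram may well settle the intent, and the benefit in error control is small. But section 2.2 names 5.2.1.2 as the place for the rules, and no diagram rescues the stated N: 18 follows directly from 5.2.1.2, and early stopping gives fewer than 12. The review board and the amendment step set neither a number treated nor an MTD criterion. The cited combination study used five doses per week after three pembrolizumab cycles, and 5.2.1.3 itself allows that IL-2 may worsen pembrolizumab's autoimmune toxicity.

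**Conclusion.** The concern holds. The prose of 5.2.1.2 gives 9 to 18 patients when all three levels open, and 3 to 12 when they do not, against a stated 12 to 15. It says what exceeds the MTD but not what establishes it, and it allows a level to be carried forward on 0 of 3. These points need no assumed DLT rate. The frequencies do: 47% to 69% of trials below 12, and 50% to 76% with three patients at the level carried forward, depend on the seven assumed profiles.

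The consequence is moderate. An upper limit of 63% after 0 of 3 is weak support for a dose meant to inform later studies, but requiring six lowers the chance of passing a level with a 30% DLT rate only from 49% to 42%. The correction should be made. Confidence is medium because the diagram could not be read.

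**What to change.** Add to 5.2.1.2: *The MTD (or Dose Level 3, if it is not exceeded) is the highest level with at most 1 patient with a DLT among 6 treated. If the level to be carried forward has only 3 patients, 3 more are treated and followed through course 1. If 2 or more of the 6 have a DLT, the next lower level is assessed the same way.*

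In section 1.0, restate N as 12 with no DLTs and a maximum of 18, possibly fewer if escalation stops before Dose Level 3. If the diagram already shows six at the last level, the new sentences only bring the prose into line with it.

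The cost is three sentences and one line, usually three more patients (needed in 50% to 76% of trials under the assumed profiles), and one more 12-week DLT window plus accrual time. Mean enrolment rises by 1.7 to 2.5 patients, mostly within the planned 12 to 15, and the chance of exceeding 15 rises from about 1% to 4% to 7%. An acceptable level passes slightly less often: 89% instead of 91% at a 10% DLT rate, and 66% instead of 71% at 20%.

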5.2.1.4 Dose Modification

Adverse events (both non-serious and serious) associated with pembrolizumab exposure may represent an immunologic etiology. These adverse events may occur shortly after the first dose or several months after the last dose of treatment. Pembrolizumab must be withheld for drug-related toxicities and severe or life-threatening AEs as per Table 4 below. See [Section 5.4.1](#) and Events of Clinical Interest Guidance Document for supportive care guidelines, including use of corticosteroids.

Dose escalations or de-escalations of pembrolizumab are not allowed.

SQ IL-2 must be withheld for drug-related toxicities and severe or life-threatening AEs as per Table 4 below. SQ IL-2 associated with AE's requiring treatment interruption can be restarted at a reduced dose not lower than a 50% reduction of the recommended 125,000 U/kg dose.

If possible, the Investigator may attribute each toxicity event to pembrolizumab or IL-2 alone with a resulting dose modification applied to a single study drug. For example, local IL-2 injection site reaction could result in a hold of SQ IL-2 dosing with pembrolizumab continued without interruption.

Patients enrolled into Dose Level 3 who require treatment interruption and meet restarting criteria as described in Table 4 may have IL-2 dosing de-escalated to Dose Level 2 for the subsequent treatment cycle or course(s). Individual patient IL-2 dosing cannot be escalated.

Table 4 Dose Modification Guidelines for Drug-Related Adverse Events

General instructions:				
Immune-related AEs	Toxicity grade or conditions (CTCAEv5.0)	Action taken to pembrolizumab	irAE management with corticosteroid and/or other therapies	Monitor and follow-up
Pneumonitis	Grade 2	Withhold	
 Administer corticosteroids (initial dose of 1-2 mg/kg prednisone or equivalent) followed by taper 	
 Monitor participants for signs and symptoms of pneumonitis Evaluate participants with suspected pneumonitis with radiographic imaging and initiate corticosteroid treatment
	Grade 3 or 4, or recurrent Grade 2	Permanently discontinue		

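### On the course-1 reading of section 5.2.1.2, one course-1 and one delayed DLT in different patients of a six-patient cohort meet neither the MTD rule nor the accrual hold

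*Combined protocol and SAP*

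**What the plan says.** Section 5.2.1.2 sets the escalation basis: "Dose-limiting toxicities (DLT's) observed in course 1 will be used to determine escalation to the next dose level". Section 5.2.1.3 agrees: "Dose-limiting toxicity (DLT) assessment will be based on events occurring during the DLT assessment period, which is defined as course 1". A course lasts 12 weeks.

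The numeric rules in section 5.2.1.2 are:

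- Expansion: "If 1 of 3 subjects in a cohort experiences a DLT, the Cohort will expand to 6 pts".
- Clearance: "If only 1 of 6 patients experiences a DLT with all patients followed for safety endpoints to the end of course 1", the next level opens.
- MTD: "If two or more patients in a cohort experience a DLT, that dose level exceeds the MTD". This sentence has no time window of its own.
- Hold: the condition is "If two or more delayed DLT's (i.e., DLT's that occur after course 1) are noted", counted per cohort. Enrolment then stops until the safety data have been analysed. Restart needs approval from the Principal Investigator and the Sponsor, and the IRB and FDA are notified.

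Delayed DLTs appear in the hold rule only. Section 2.1 allows up to three courses, so up to 24 of 36 treatment weeks lie outside the DLT window. On adverse events associated with pembrolizumab, section 5.2.1.4 adds: "These adverse events may occur shortly after the first dose or several months after the last dose of treatment".

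**The concern.** The two counts run side by side and are never added. A cohort reaches six patients only after a course-1 DLT. If each affected patient has a single event, the hold at such a level then needs two further affected patients, three in all. With one further patient affected, no rule responds, although two delayed DLTs with no course-1 DLT would hold accrual.

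The case can arise before the escalation decision as well as after it. When a cohort expands after 1 of 3, the first three patients may be in course 2 or 3 while the added three are still in course 1. A delayed DLT in the first group could be known when the cohort is judged, and on the course-1 reading the next level still opens. From Dose Level 2 to Dose Level 3 the IL-2 dose rises from 72,000 to 600,000 U/kg (Table 1), about 8.3-fold. What is at stake is whether accrual at the higher level pauses for a formal look at the level below, or continues unless someone chooses to intervene.

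**Working it through.** The plan states no DLT rate or error rate for these rules, so there is no figure to reproduce. The check has two parts.

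**1. Which combinations trigger a rule.** Let a be the number of patients with a course-1 DLT and b the number of other patients with one delayed DLT each.

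| a | b | MTD rule, course-1 reading (a ≥ 2) | Hold rule (b ≥ 2) | MTD rule, any-time reading (a + b ≥ 2) |
|---|---|---|---|---|
| 0 | 1 | no | no | no |
| 0 | 2 | no | yes | yes |
| 1 | 0 | no | no | no |
| 1 | 1 | **no** | **no** | yes |
| 1 | 2 | no | yes | yes |
| 2 | 0 | yes | no | yes |

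Rows with a = 0 belong to three-patient cohorts, because expansion needs a course-1 DLT. On the course-1 reading, (1, 1) is the only row with two or more affected patients and no trigger.

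The last column shows why the untimed MTD sentence does not settle the matter. Read literally, it closes the (1, 1) gap. It also makes (0, 2) exceed the MTD, while the hold rule lets accrual restart after approval in that same case.

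**2. How often the gap would arise.** Let p be the course-1 DLT probability per patient and d the delayed DLT probability in each of the five patients without a course-1 DLT. Both are assumptions, each varied over 0.1, 0.2 and 0.3. Patients are taken as independent, all five are at the full risk d, and the patient with the course-1 DLT has no delayed DLT.

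A cohort ends course 1 at 1 of 6 by having 1 of 3 and then 0 of 3:

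P(1 of 6) = 3p(1−p)² × (1−p)³ = 3p(1−p)⁵

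- p = 0.1: 0.177
- p = 0.2: 0.197
- p = 0.3: 0.151

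Given that, the chance of exactly one delayed DLT among the other five is 5d(1−d)⁴:

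- d = 0.1: 5 × 0.1 × 0.6561 = 0.328
- d = 0.2: 5 × 0.2 × 0.4096 = 0.410
- d = 0.3: 5 × 0.3 × 0.2401 = 0.360

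The chance per dose level is the product. The lowest is 0.1513 × 0.3281 = 0.050 (p = 0.3, d = 0.1). The highest is 0.1966 × 0.4096 = 0.081 (p = 0.2, d = 0.2).

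**3. Effect of a combined count.** For a cohort at 1 of 6, the existing hold needs two or more delayed DLTs. A combined patient count of two needs one or more among the other five, with probability 1 − (1−d)⁵.

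| d | Existing hold | With combined count |
|---|---|---|
| 0.1 | 8% | 41% |
| 0.2 | 26% | 67% |
| 0.3 | 47% | 83% |

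The difference in each row is the gap probability from part 2, up to rounding.

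**The case against.** The strongest reply is that this is a deliberate design. A fixed first-course window is a legitimate basis for escalation. Delayed DLTs accrue over a longer and less uniform period, so a different threshold for them is defensible. One course-1 plus one delayed DLT is therefore not simply the same evidence as two course-1 DLTs, and the point does not rest on treating them as equal. In addition, section 5.2.1.4's remark on late onset concerns pembrolizumab, which stays at 200 mg at every level. A late pembrolizumab event is not by itself evidence about the IL-2 level, although section 5.2.1.3 says IL-2 may exacerbate such toxicity. All of this stands.

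A reader might infer that nothing at all happens in the mixed case. The documents do not support that. Under section 8.1.1 the SDRB meets after each dose-level cohort, and as needed for unanticipated events, and directs escalation from all collected safety data. Section 7.3.3.1 requires serious events up to 90 days after treatment (or until new anti-cancer therapy starts, if earlier) to reach the Sponsor within 24 hours. Section 8.1.2 provides DSMC and IRB review at least annually and as needed. Section 5.8 lists the severity of adverse reactions among the termination criteria. None of these carries a combined number, so review remains but a hold is not forced.

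A reader might also infer that a higher level would always be exposed. That cannot happen at Dose Level 3, which has no level above it. Section 2.3 makes any expansion cohort there conditional on data and safety analysis and a protocol amendment.

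**Conclusion.** The point holds as a gap between two numeric rules. On the course-1 reading, which sections 5.2.1.2 and 5.2.1.3 both favour, one course-1 DLT and one delayed DLT in different patients trigger neither. The untimed MTD sentence leaves the text ambiguous and does not rescue it, because the literal reading collides with hold-and-restart.

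Under assumed course-1 and delayed rates of 10-30%, about 5-8% of dose levels would fall in the gap. The 33-41% figure applies only to cohorts that have already ended course 1 at 1 of 6 and should not be read as the frequency across cohorts. Both ranges rest on assumed rates and on independence between patients. Patients who stop early, for instance for progression, would have less time at risk than the calculation allows. The figures show the order of size and are not a forecast. The change is worth making because it is small and concerns safety. The gap does not invalidate the escalation design.

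**What to change.** In section 5.2.1.2, keep the existing hold for two or more delayed DLTs. Add that accrual is also held, for the same safety analysis and with the same restart approvals, when course-1 and delayed DLTs together affect two or more patients in a dose-level cohort.

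The new trigger should be added and should not replace the old one. The present hold counts events and the MTD rule counts patients. Two delayed DLTs in one patient hold accrual today, and a patient count alone would lose that trigger.

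Also state that the MTD sentence refers to course-1 DLTs, or otherwise reconcile it with the hold rule.

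The change needs about two sentences and no extra patients or procedures. The real cost is more pauses in cohorts that already had one DLT: under the assumed rates, the chance of a later hold in a cohort at 1 of 6 rises as shown in part 3 of the working. Each pause needs Principal Investigator and Sponsor approval to end, with IRB and FDA notification, in a trial of 12 to 15 patients.
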